9.11. Definition of End of Study

The end of study is the point at which all the study data has been entered and queries resolved including the data generated from the laboratory analyses.

10. SAFETY REPORTING

Safety reporting is applicable to this study, and the safety reporting window will be from time of consent, until the point that the participant completes the study (i.e., attends the week 24 visit). Investigator follow up of SAEs will be until participant completion of the study.

10.1. Definitions

Definition of Adverse Event (AE)

Any untoward medical occurrence in a clinical trial participant.

Definition of Serious Adverse Events

A serious adverse event is any untoward medical occurrence that:

- results in death
- is life-threatening
- requires inpatient hospitalisation or prolongation of existing hospitalisation
- results in persistent or significant disability/incapacity
- consists of a congenital anomaly or birth defect.

Other 'important medical events' may also be considered a serious adverse event when, based upon appropriate medical judgement, the event may jeopardise the participant and may require medical or surgical intervention to prevent one of the outcomes listed above. This includes 'transmission of infectious agents via a medicinal product' if this does not fall into one of the other categories specified above. NOTE: The term "life-threatening" in the definition of "serious" refers to an event in which the participant was at risk of death at the time of the event; it does not refer to an event which hypothetically might have caused death if it were more severe.

10.2. Reporting Procedures for Serious Adverse Events

Sites are required to report to the OPTIMISE trial team only those SAEs that are related to trial intervention (i.e. secukinumab or adalimumab) or trial procedures. These SAEs must be reported within a very short period of time and under no circumstances should this exceed 24 hours following knowledge of the SAE.

Causality of the SAE with respect to trial intervention/procedures must be assessed by medically qualified doctor according to the following definitions, however this may be missing at the time of the initial report of the SAE:

Classification	Relationship	Definition
		Starts within a time related to the trial drug administration
	Almost certainly	and
		No obvious alternative medical explanation.
		Starts within a time related to the trial drug administration
	Probably	and
Related	FIODADIY	Cannot be reasonably explained by known characteristics of
		the participant's clinical state.
	Possibly	Starts within a time related to the trial drug administration
		and
		A causal relationship between the trial drug and the
		adverse event is at least a reasonable possibility.
		The time association or the participant's clinical state is
Not related	Unlikely	such that the trial drug is not likely to have had an
		association with the observed effect.
	Unrelated	The AE is definitely not associated with the trial drug
	Unrelated	administered.

SAEs are to be reported to the OPTIMISE trial team via completion of the OPTIMISE SAE form, which should be scanned and emailed to: [contact]. Receipt will be acknowledged within 1 working day.

Expectedness will be determined by the Nominated Person at OCTRU on behalf of the Sponsor. Expectedness for events reported as related to adalimumab or secukinumab will be determined in relation to the version of the SmPC specified in the REC application for these drugs.

SAEs reported as related to other trial procedure will be deemed as unexpected.

A serious adverse event (SAE) occurring to a participant will be reported to the REC that gave a favourable opinion of the study where in the opinion of the Chief Investigator the event was 'related' (resulted from administration of any of the research procedures include study drug treatment) and 'unexpected' in relation to those procedures. Reports of related and unexpected SAEs will be submitted within 15 working days of the Chief Investigator becoming aware of the event, using the HRA report of

serious adverse event form (see HRA website). This will be undertaken by the OPTIMISE trial team at OCTRU.

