Currently in clinical practice we select either TNF or IL-17A inhibitors for patients with moderate-severe active PsA based on a limited clinical phenotype (differentiation in psoriasis has been shown), comorbidities, personal experience and cost. In the UK, most patients currently receive TNF inhibitors first line, presumably due to longer term data, physician familiarity and lower cost using biosimilars. However, the Th17 pathway is significantly upregulated in PsA. Th17 cells are a subset of pro-inflammatory T helper cells defined by their production of IL-17, thus suggesting that treatment with IL-17 inhibitors in some individuals could improve outcomes. The lack of data informing the choice of biologics is frustrating for clinicians and for patients who want to know which therapy would be best for them. There has not been a James Lind priority setting partnership (PSP) for PsA however in the recent Psoriasis PSP the question "What factors predict how well psoriasis will respond to a treatment?" was ranked 3rd in the top ten unmet needs. This highlights the importance that both patients and clinicians ascribe to the issue.

It is increasingly recognised that to optimise quality of life and functional ability, treatment should be focused on achieving a treatment target, such as MDA. Patients who achieve MDA have less joint damage as measured using x-rays, better quality of life and function¹⁰. Thus optimising an individual's

OPTIMISE_Protocol_V5.0_17Jun2022.docx

Clinical Research Protocol Template version 15.0

© Copyright: The University of Oxford and Oxford University Hospitals NHS Foundation Trust 2019

Page 14 of 43

outcomes, requires the ability to predict which biologic has the greatest chance of that individual achieving MDA and then utilising this precision medicine approach in routine clinical practice.

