9.8.2. Week 12 or 16 – all sites

Participants will attend at week 12 (TNFi [adalimumab] treated patients) or 16 (IL-17Ai [secukinumab] treated patients) in line with routine care. The following will be performed at the visit for the purpose of the study:

Update of medical history (5 mins):

Where not undertaken as part of standard care:

- Confirm any key changes in their medical history
- Record change in concomitant medication (glucocorticoids and non-steroidal anti-inflammatory drugs only).
- Experience of any key side effects to medication

Composite Clinical Outcome Measures (20 mins plus 30 min for questionnaire completion)

• as baseline assessment (screening visit) – see section 9.3.

Medication compliance (2 mins)

• Any patient-reported missed doses of treatment will be recorded.

The study visit would take ~60 minutes compared to 15 minutes for a routine care visit.

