13.3.2. Data and Safety Monitoring Committee

The Data and Safety Monitoring Committee (DSMC) will monitor accruing data, study conduct and safety of the participants. The DSMC will also undertake a blinded interim review of the data to ensure that the assumed response rates overall are as expected. The DSMC will meet at least annually during the recruitment period.

A DSMC Charter will describes the membership, remit and responsibilities of this committee.

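### SAE reporting is limited to events an unblinded doctor judges related, so SAEs judged not related have no assured route to the trial team or DSMC, and the protocol's sections disagree on which adverse events are collected

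*Protocol*

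**What the plan says.** All references are to the protocol; no SAP or DSMC charter is at hand.

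- **Reporting rule (10.2).** "Sites are required to report to the OPTIMISE trial team only those SAEs that are related to trial intervention" or to trial procedures, within 24 hours of knowledge. Related covers three grades, down to Possibly. Unlikely and Unrelated count as not related.
- **Who judges (10.2).** "Causality of the SAE with respect to trial intervention/procedures must be assessed by medically qualified doctor", with the qualification "however this may be missing at the time of the initial report of the SAE".
- **Blinding (7, 9.4, 9.5).** Therapy is not blinded, and relevant study personnel are emailed the allocation. The only blinded clinical assessment described is that of the primary clinical measures.
- **Definition (10.1).** An adverse event is "Any untoward medical occurrence in a clinical trial participant", with no reference to causality. The SAE definition has no causality condition either.
- **Visits (9.8.2, repeated at week 24 by 9.8.3).** Sites record "Experience of any key side effects to medication", and also confirm key changes in medical history. Appendix B marks adverse event assessments at weeks 12, 16 and 24 without restriction.
- **Withdrawal (9.10).** The type of withdrawal and its reason, if known, go in the CRF. An adverse event is one of the listed reasons.
- **Oversight (13.3.2).** The DSMC "will monitor accruing data, study conduct and safety of the participants". Sections 11.5 and 11.6 plan no formal comparative interim analysis and no stopping rules.

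**The concern.** A relatedness filter at the site decides which SAEs are certain to be seen centrally. Many serious events, such as infections, cancers or cardiac events, also occur without the drug. A single case can reasonably be judged unlikely to be related, and an excess may show only when all such events are counted by arm. If the cases judged not related are not collected in a defined way, that count cannot be made later. An SAP or charter can specify tables, but it cannot recover events that sites were never required to send.

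The judgement is also made knowing the drug. Section 5 says most UK patients currently receive TNF inhibitors first line, "presumably due to longer term data, physician familiarity and lower cost using biosimilars". If familiarity also affected how readily a doctor calls an event related, related-only counts would mix true risk with attribution habit. Nothing in the protocol guards against this.

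Finally, a site reading 10.1, 9.8.2, 10.2 and Appendix B together cannot tell which adverse events it must record.

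**Working it through.** **1. The sections side by side**

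| Place | What is captured | Causality condition |
|---|---|---|
| 10.1 | AE and SAE definitions | None |
| Appendix B | Adverse event assessments, weeks 12, 16, 24 | None stated |
| 9.8.2, 9.8.3 | Key side effects of medication | Yes |
| 9.8.2, 9.8.3 | Key changes in medical history | None, but not described as SAE capture |
| 9.10 | Reason for withdrawal, if known | None, but only for those who withdraw |
| 10.2 | SAE reports to the trial team | Related only |

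Take a hospital admission judged unlikely to be related. It meets the SAE definition in 10.1 but need not be reported under 10.2. It is not a side effect under 9.8.2. It might be entered as a medical history change, or under the Appendix B row, but no section says that it must be recorded as an SAE. Section 9.10 adds a gap: one sentence says no further study visits are required after stopping treatment, while its closing paragraph says follow-up need not stop. Those who stop early may therefore miss the visit questions.

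**2. Tension inside 10.2**

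Relatedness is the condition for reporting, yet causality may be missing when the report is made. The section does not say whether an SAE not yet assessed is reportable.

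**3. Size**

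The protocol gives no SAE rate and no attribution figure, so there is no stated figure to reproduce. The only protocol input below is 212 per arm (Synopsis). The risk r and the probability q of being judged related are assumptions, chosen to show the mechanism.

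Expected SAEs per arm = 212 × r. Expected reports = 212 × r × q. Here the true risk is equal in both arms, with q = 0.30 in one and 0.60 in the other.

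| Assumed r | SAEs per arm | Reported, q = 0.30 | Reported, q = 0.60 |
|---|---|---|---|
| 3% | 6.4 | 1.9 | 3.8 |
| 5% | 10.6 | 3.2 | 6.4 |
| 10% | 21.2 | 6.4 | 12.7 |

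- The apparent ratio is 0.60 / 0.30 = 2.0 at every r. It comes entirely from the assumed q. Pairs of 40% v 60% and 20% v 50% give 1.5 and 2.5.
- The share not reported is 1 − (0.30 + 0.60)/2 = 55%.
- With q = 0.50 in both arms the ratio is 1.0, but half of the SAEs are not reported.

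The chance of at least one report in an arm, for a harm with assumed risk 1%, is 1 − (1 − 0.01q)^212:

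- q = 1: 88%
- q = 0.50: 65%
- q = 0.25: 41%

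The loss of information therefore does not depend on the arms differing. A spurious ratio does.

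**The case against.** The strongest reply is that related-only reporting is a deliberate and openly stated choice. Both drugs are licensed, NICE approved and given at the usual licensed dose. The threshold is low, since Possibly needs only compatible timing and a reasonable possibility of causation. There is no safety objective, and section 11.3 disclaims interest in a treatment effect as such. Safety is also overseen by the Trial Steering Committee and a monitoring plan, and investigators can discontinue treatment and follow up adverse events. Most of this stands, and it justifies keeping expedited reporting for related SAEs only. It does not show that SAEs judged not related are recorded anywhere as SAEs.

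A reader might infer more than the text supports:

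- **That visits ask only about drug side effects.** They do not. Medical history changes and the unrestricted Appendix B row are also there.
- **That the DSMC's comparison of the two drugs is biased.** No such comparison is described, and the charter is not shown.
- **That no event judged unrelated can ever reach the trial team.** One reported before causality is assessed could, and 10.2 does not forbid sites from sending others.
- **That attribution does differ by arm.** Section 5 speaks of familiarity as a presumed reason for prescribing, not of causality assessment.
- **That the harms named in 8.3 would be missed.** That is an eligibility list, and possibly related cases are reported.
- **That related SAEs would be out by a factor of two.** That figure is just the assumed 60/30.

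**Conclusion.** The point holds as a gap in assured SAE capture and an inconsistency between sections. Under 10.2, deaths and hospitalisations judged unlikely to be related or unrelated have no assured route to the trial team or the DSMC. The judgement that decides this is made without any provision for blinding. Sections 10.1, 9.8.2, 10.2 and Appendix B do not agree on what is collected.

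The documents do not allow the loss to be sized, and the figures above rest wholly on assumed risks and attribution probabilities. Differential attribution remains a possibility. The consequence is for the description and monitoring of safety. The primary MDA interaction analysis does not use these data and is unaffected. The change is worth making because it is cheap and because unrecorded events cannot be recovered dependably at the analysis stage.

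**What to change.** 1. Reconcile 9.8.2, 9.8.3, 10.1, 10.2 and Appendix B so that they state one rule for what is recorded and one for what is expedited. Say in 10.2 how an SAE without a causality assessment is handled.
2. Keep 24-hour reporting for related SAEs.
3. State that every SAE as defined in 10.1 is recorded on the eCRF, whatever its causality, at the existing week 12/16 and week 24 adverse event assessments. Record it also on the existing withdrawal record, so that deaths and early stoppers are covered. Hold causality as an attribute of the event, not as a condition for recording it.
4. Give the DSMC, and report at the end, an all-cause SAE table by arm beside the related-only table.

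The cost is a little more site data entry and one extra table. No new visit, expedited report or change to treatment is needed.

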10.3. Contraception & Pregnancy

Contraception advice is to be given as per standard of care.

In the event that a trial participant becomes pregnant, the pregnancy is to be managed as per standard of care.

Pregnancy does not require to be reported to the OPTIMISE trial team other than in the unexpected occurrence of a pregnancy with an unfavourable outcome (congenital abnormality or birth defect) which is deemed related to trial treatment, in which case this requires to be reported as a SAE.

11. STATISTICS AND ANALYSIS

11.1. Statistical Analysis Plan (SAP)

The statistical aspects of the study are summarised here with details fully described in a statistical analysis plan that will be available from the time that the first participant is recruited. The SAP will be finalised before any analysis takes place.

11.2. Description of the Statistical Methods

The primary clinical response outcome will be the achievement of the MDA criteria. This is a dichotomous composite criteria including clinical outcomes (tender joint count, swollen joint count, enthesitis count and psoriasis score) and patient reported outcomes (patient global score, patient pain score and function measured by the HAQ. To be classified as being in MDA, patients must achieve 5 or more of the criteria given below:

Domain	Measure Used	Criteria for assessing MDA
Peripheral arthritis	Tender joint count (68)	≤1
Peripheral arthritis	Swollen joint count (66)	≤1
Enthesitis	Enthesitis count (LEI and SPARCC)	≤1
Psoriasis	PASI	≤1
Pain	Patient pain VAS	≤15mm
Global disease activity	Patient global VAS	≤20mm
Function	HAQ	≤0.5

The proportion of patients achieving the criteria in the Th17 high vs Th17 low groups will be compared within treatment arms. Primary analysis will be logistic regression adjusted for Th17 as a binary indicator, treatment and an interaction between the 2. We will also adjust for the stratification factors study centre and psoriasis severity. A random effect will be included to account for any heterogeneity in the response due to recruitment centre, with the other variables being incorporated as fixed effects. Primary focus is on the interaction between biomarker and treatment, we will report the p-value for this

OPTIMISE_Protocol_V5.0_17Jun2022.docx

Clinical Research Protocol Template version 15.0

© Copyright: The University of Oxford and Oxford University Hospitals NHS Foundation Trust 2019

interaction and consider a p-value < 0.05 as significant. We will report the mean response rate by treatment and also for each of the 4 strata defined by treatment and biomarker along with 95% CI. Analysis will be on an intention to treat basis, that is according to group randomised to irrespective of compliance with treatment allocation.

In phase 2, additional hypothesis generating analyses will be undertaken to investigate alternative potential models for predicting response to different classes of biologic. This large dataset will be used to model response rates adjusting for other variables (for example: different therapies (TNFi vs IL-17i), standard care (the therapy originally planned by the recruiting physician), alternate cut-off points of Th17 proportions, Th17 proportions as a continuous measure or alternative laboratory measures of immunophenotype including transcriptomics. We will be able to use the models developed to predict what outcomes would be expected from a precision medicine based clinical pathway. This could then be validated in a future study.

In phase 3, we will use the immunophenotyping and transcriptomic data generated to gain mechanistic insight into genes and pathways that underpin the clinical response. Analysis of paired flow cytometry samples before and after treatment in each arm will allow us to understand the stability of the Th17 compartment in MDA responders and non-responders. This question is especially pertinent in view of data suggesting the intracellular IL-17A signature increases after treatment with TNF blockade [25, 43]. Similarly, we will use the RNA sequencing data to look at immune subset-specific differential gene expression from Th17-high, anti-IL-17A responders and refractory patients and TH17-low anti-TNF responders and refractory patients. Genes identified will be validated in the whole blood RNA sequencing data-set and we will use network and pathway analysis to identify key nodes of refractory disease which can be validated in future mechanistic studies.

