9.4. Randomisation

Once all eligibility data and immunophenotyping results are available, randomisation will be performed centrally by CTU staff following confirmation of eligibility from study site personnel, using the OCTRU randomisation system. Patients will be randomised in a 1:1 allocation ratio to either TNF or IL-17A inhibitors and these drugs will be prescribed open label as in routine care. The randomisation will use a minimisation algorithm to ensure balanced allocation across the treatment groups, stratified by activated Th17 proportion (\leq />1.58%), psoriasis severity (PASI < or \geq 10) and study centre. The minimisation algorithm will include a probabilistic element and a small number of participants randomised by simple randomisation at the start of the trial to seed the algorithm in order to ensure the unpredictability of treatment allocation. Patients will be contacted by telephone to confirm continued consent to participate and to advise them of their treatment allocation.

There is no blinding of therapy allocation so no allocation code or code-breaking procedure is required. All relevant study personnel will be informed of the treatment allocation by email.

Following randomisation the GP letter must be sent by the site team to the participant's GP to notify them of study participation and treatment allocation.

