9.7. Baseline Assessments

Baseline clinical assessments and questionnaires will be completed at the screening visit and will be used to measure pre-treatment disease activity.

Following the screening visit, eligibility will be confirmed for the study and randomisation will be performed as outlined in section 9.4. The patient will be informed of the drug that they have been randomised to and a routine NHS prescription for that drug (either adalimumab or secukinumab) will be submitted by the clinical care team. Treatment will be started following standard NHS procedures (which usually takes 3-4 weeks from the prescription being written). In most cases, this will mean that NHS drug supply will be delivered to the patient by an approved healthcare delivery company to ensure temperature control. The patient will be trained how to perform the injections themselves and how to safety dispose of any sharps as per usual practise at each participating site. This may be done by telephone or video call as per usual practise at each participating site. The patient will administer the treatment themselves.

The baseline date will be the date that the drug is first administered.

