11.3. Sample Size Determination

This study has been powered to test for a biomarker-treatment interaction in response as defined by achievement of the MDA criteria at 24 weeks. Based on RCT and registry data for both drugs $^{10\,24\,25}$, we expect similar non-biomarker stratified MDA response rates in each treatment arm in the RCT and estimate the MDA response rate overall to be ~50%.

A total of 424 participants will be randomised. Based on 10,000 simulations, this study sample size has 98% power and 5% (2-sided) significance to detect a biomarker-treatment interaction. This assumes the proportion of MDA responders is 60% and 40% for participants with low/high Th17 treated with TNFi, and 40% and 60% for participants with low/high Th17 treated with IL-17Ai. This equates to a relative interaction effect of 0.2. A further assumption is that the baseline activated Th17 levels (high versus low) will be split 50:50. Using the same design and methodology as the Japanese study, we have refined the cut-off point proposed for this study. The cut point has been set as the median level in our UK analysis , thus we estimate that around 50% of patients will have high Th17 proportions. As patients are randomised 1:1 to the different treatments, this should result in around 106 patients randomised to each biomarker-treatment combination (namely Th17 high plus TNF inhibitor, Th17 high plus IL-17A inhibitor, Th17 low plus TNF inhibitor, Th17 low plus IL-17A inhibitor). This sample size also includes a loss-to-follow-up of 10%. The power for different effects of biomarker and treatment are given in the table, where the power for the first row is equivalent to the 2-sided error rate. The rest of the table shows the power for varying degrees of interaction, with the last 2 rows showing scenarios when there is

a biomarker effect but it is in the same direction for both treatments, i.e. when there is no treatment biomarker interaction.

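### The primary model adjusts for baseline disease only through PASI cut at 10; pre-specifying a few baseline MDA components that are already collected would be a cheap improvement

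*Protocol*

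**What the plan says.** Protocol section 11.2 gives the model terms: "Primary analysis will be logistic regression adjusted for Th17 as a binary indicator, treatment and an interaction between the 2". It continues: "We will also adjust for the stratification factors study centre and psoriasis severity". Centre enters as a random effect and everything else as a fixed effect. Section 9.4 defines the psoriasis stratum as PASI below 10 against 10 or above.

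Section 11.2 also defines MDA as meeting at least five of seven thresholds: tender joints, swollen joints, enthesitis and PASI each at most 1, pain VAS at most 15 mm, patient global VAS at most 20 mm, and HAQ at most 0.5. Section 9.3 lists all seven measures at screening, and section 9.7 states their purpose: "Baseline clinical assessments and questionnaires will be completed at the screening visit and will be used to measure pre-treatment disease activity".

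Section 11.3 expects a higher MDA rate than a published head-to-head trial because this trial's patients should start with fewer active joints and milder psoriasis. Other covariates appear only in the hypothesis-generating second phase (11.2) and in the exploratory predictive model (section 6). Section 11.8 intends a complete-case analysis.

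**The concern.** Because MDA is an absolute state and not a change from baseline, a patient's starting level should help to predict who reaches it. The Protocol relies on this in section 11.3 to defend its assumed response rate, yet leaves baseline joint counts out of the model for that response. Tender and swollen joint counts, enthesitis, pain, global VAS and HAQ are all absent. PASI is present only as a split at 10, far from its MDA threshold of 1.

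In a logistic model, adjusting for a prognostic baseline variable moves the treatment and interaction log odds ratios further from zero by more, in proportion, than it raises their standard errors, so power rises. What is at stake is mainly power for interactions smaller than the design effect. A second matter is the comparison of Th17 high with Th17 low inside each arm, which 11.2 also plans. Th17 level is not randomised, so those contrasts can be confounded by baseline activity.

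**Working it through.** **Inputs from the Protocol**
- Section 11.3: "this study sample size has 98% power and 5% (2-sided) significance to detect a biomarker-treatment interaction".
- Cell rates in the TNFi arm, section 11.3: "This assumes the proportion of MDA responders is 60% and 40% for participants with low/high Th17 treated with TNFi". The IL-17Ai arm is given the mirror image, 0.40 when Th17 is low and 0.60 when it is high.
- Biomarker split, section 11.3: "the baseline activated Th17 levels (high versus low) will be split 50:50".
- Allocation, section 9.4: "Patients will be randomised in a 1:1 allocation ratio to either TNF or IL-17A inhibitors".
- The power table in 11.3 uses 388 analysed, so 388 / 4 = 97 per cell.

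**Step 1: reproduce the Protocol's power.** The test is a two-sided Wald test of the interaction log odds ratio d:

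d = [logit(IL-17Ai high) − logit(IL-17Ai low)] − [logit(TNFi high) − logit(TNFi low)]

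SE = √( Σ over four cells of 1 / (97 p(1−p)) ); power ≈ Φ(|d|/SE − 1.96)

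- Design effect (0.4/0.6 v 0.6/0.4): d = 0.811 + 0.811 = 1.622; SE = √(4 / (97 × 0.24)) = 0.4145; d/SE = 3.913; power = Φ(1.953) = 97.5%. The Protocol gives 98.06%.
- Smaller effect (0.4/0.6 v 0.55/0.45): d = 0.811 + 0.401 = 1.212; SE = 0.4114; d/SE = 2.947; power = Φ(0.987) = 83.8%. The Protocol gives 83.68%.
- One-arm effect (0.4/0.6 v 0.5/0.5): d = 0.811; SE = 0.4103; d/SE = 1.976; power = Φ(0.016) ≈ 50.7%. The Protocol gives 50.14%.

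The stated figures are reproduced, so the same set-up can carry the adjusted analysis.

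**Step 2: add a baseline score.** One standard-normal score z stands in for the combined baseline components, with logit P(MDA) = a(cell) + b·z. Each a(cell) is solved so that the cell rate stays at the Protocol's value. The slope b is 0.3, 0.5, 0.8 or 1.2. **These strengths are assumptions**; they correspond to an AUC of about 0.58, 0.63, 0.70 and 0.77, or about 2%, 5%, 12% and 21% of outcome variance. For each setting, 10,000 trials of 388 were simulated, and the interaction was tested on the same data without and with z.

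| Scenario | AUC 0.58 | AUC 0.63 | AUC 0.70 | AUC 0.77 |
|---|---|---|---|---|
| Design effect | 97.6→98.0 | 97.9→98.4 | 97.7→98.8 | 97.8→99.5 |
| Smaller effect | 83.6→84.9 | 84.1→86.6 | 84.6→89.0 | 83.9→92.2 |
| One-arm effect | 50.5→52.3 | 49.7→52.7 | 50.8→56.9 | 49.8→60.7 |

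Gains in points, from the unrounded results:
- Design effect: 97.95 − 97.64 = 0.3, up to 99.49 − 97.83 = 1.7.
- Smaller effect: 84.90 − 83.64 = 1.3, up to 92.18 − 83.94 = 8.2.
- One-arm effect: 52.28 − 50.54 = 1.7, up to 60.70 − 49.79 = 10.9.

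With no true interaction, the adjusted test rejects in 4.6% to 5.1% of trials.

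**Step 3: limits of the simulation.** A score with no predictive value (b = 0) still moves the one-arm figure from 49.68 to 50.37, or 0.7 points, so the gains at the weak end are barely distinguishable from none. Neither centre nor the PASI stratum was simulated. The Protocol's model already contains both and may already capture part of the gain. The single score also has a known linear form, whereas real covariates need several estimated and correlated terms.

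**The case against.** The strongest defence is that 11.2 gives a coherent pre-specified model built from the minimisation factors, that 11.1 leaves details to an SAP not shown here, and that a 20-point difference is the stated target, for which power is already about 98%. The last part stands: at the design effect there is little to gain. The appeal to the SAP is weaker, because 11.2 names its covariates and so fixes the choice on its face.

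Four stronger readings are tempting, and the Protocol supports none of them.
- *That the model ignores baseline MDA components altogether.* It does not: PASI enters through the psoriasis stratum, though only cut at 10.
- *That the trial is underpowered without the adjustment.* The Protocol's power table reproduces, and the powers of about 84% and 50% belong to effects smaller than the design effect.
- *That the primary interaction test is confounded by baseline activity.* Treatment is randomised with Th17 as a minimisation factor, so the treatment contrast within each Th17 level is protected. The aim is also prediction, and a marker that predicts partly through correlated disease activity still predicts. Baseline main effects would not in any case deal with other effect modifiers that travel with Th17. The confounding argument reaches only the within-arm high v low contrasts.
- *That adjustment is free.* It uses a few degrees of freedom and makes the interaction odds ratio conditional on the covariates. Under the complete-case rule in 11.8 it would drop patients with a missing baseline value unless a rule is set.

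**Conclusion.** The point holds as a cheap improvement, not as an error that threatens the primary result. Baseline disease is adjusted for only through dichotomised PASI, while six of the seven components are collected and unused in the primary model, and the Protocol's own reasoning treats one of the omitted domains (joint counts) as prognostic. The benefit is negligible at the design effect. It could be useful for smaller or one-arm interactions, where the Protocol concedes lower power, if the baseline components predict MDA at least moderately: at an assumed AUC of 0.70 the gain is about 4 points in the 84% scenario and 6 points in the 50% scenario. All sizes rest on the assumed AUC range of 0.58 to 0.77 and on a simulation without centre or the PASI stratum, so the real gain may be somewhat smaller. Whatever the power gain, adjustment also reduces confounding by baseline activity in the within-arm Th17 contrasts.

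**What to change.** In section 11.2, with the SAP aligned, pre-specify a few continuous baseline covariates as main effects in the primary model: for example HAQ, patient pain VAS, tender joint count on a log or square-root scale, and PASI as a continuous variable. State a simple imputation rule for missing baseline values, so that the complete-case rule in 11.8 removes nobody for a missing covariate. Report the four treatment-by-Th17 response rates by standardisation over the observed covariates, so that they stay on the population scale that 11.2 already plans to report.

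The cost is a sentence or two of text and about four model terms. No visit, measurement or patient is added. Section 11.1 says that the SAP will be finalised before any analysis, so the change can be pre-specified. The report should state that the interaction odds ratio is conditional on the covariates.
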